AV7909: Three consecutive lots of AV7909 vaccine (containing 0.5 mL AVA + 0.25 mg CPG 7909 adjuvant per dose) are to be administered IM on Days 1 and 15 in Groups 1 to 3, respectively.

Placebo (saline for injection): Saline for injection will be administered SC on Day 29 in Groups 1 to 3 to mask the vaccine schedule.

Duration of Treatment:

Three vaccinations will be administered two weeks apart.

Reference Therapy, Dosage and Mode of Administration:

BioThrax (Anthrax Vaccine Adsorbed [AVA]): In Group 4, one lot of BioThrax (containing 0.5 mL AVA per dose) is to be administered subcutaneously (SC) on Days 1, 15, and 29.

Criteria for Evaluation:

Primary:

Lot Consistency:

- Equivalent immunogenicity across three consecutive AV7909 lots as demonstrated by the 95% confidence interval (CI) for the ratios of geometric mean TNA NF₅₀ at Day 64 for each of the three lot-to-lot comparisons to be within 0.5 and 2.0.
- Protective level of immunogenicity in all three consecutive AV7909 lots as demonstrated by the lower bound (LB) of the two-sided 95% CI to be $\geq 40\%$ for the proportions of AV7909 subjects in each of the three lots achieving a TNA NF₅₀ ≥ 0.56 at Day 64. For this endpoint, the threshold of protection (0.56) is based on the Day 70 TNA NF₅₀ value associated with 70% survival in rabbits administered BioThrax on Days 0 and 28 and challenged on Day 70 with *Bacillus anthracis* spores (Study 646).

Immunogenicity:

- Lower bound of the two-sided 95% CI is $\geq 40\%$ for the proportion of AV7909 participants in Groups 1-3 (three lots pooled) achieving a TNA NF₅₀ ≥ 0.56 on Day 64.
- Non-inferiority of AV7909 to BioThrax at Day 64 as determined by the two-sided lower 95% CI of the difference in the proportion of AV7909 participants (three lots pooled) with a TNA NF₅₀ ≥ 0.29 and the proportion of BioThrax participants with a TNA NF₅₀ value ≥ 0.29 being greater than -15%. For this endpoint, the threshold of protection (0.29) is based on the Day 70 TNA NF₅₀ value associated with 70% survival in nonhuman primates (NHPs) administered BioThrax on Days 0 and 28 and challenged on Day 70 (Study 844).

Safety:

- Incidences of SAEs from the time of the first vaccination on Day 1 through the 12-month safety follow-up telephone call following the last vaccination.

Secondary:

Immunogenicity:

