7.3.1. Discontinuation of Vaccination

Vaccinations will be permanently discontinued in participants who meet the individual participant halting rules in [Table 5](#). The date and reason for discontinuation of vaccination is to be recorded on the eCRF.

Participants who have received at least one vaccination will be encouraged to participate in all remaining study visits (for safety assessments only) and safety follow-up calls through Month 13. A participant who complies with safety-only assessments after prematurely discontinuing vaccinations will be considered to be continuing in the study. Participants who are being followed for safety only will not be required to have any further TNA blood draws and assessments associated with vaccination (eg, vital signs evaluation occurring 30 ± 5 minutes after vaccination and e-diary). However, e-diary entries associated with a past vaccination and site review of those entries must still be completed (refer to [Section 8.3.5.1](#)).

If a participant who has received at least one vaccination discontinues treatment prematurely but refuses to continue with safety-only follow up, the participant must be withdrawn from the study, with the reason for study withdrawal recorded on the eCRF (refer to [Section 7.3.2](#)). If the refusal to participate in safety-only follow-up procedures occurs before Day 64, the participant will be requested to attend an EWV for a final in-clinic safety assessment before being withdrawn from the study (refer to EWV procedures under [Section 8.1.7](#)).

Table 5: Criteria for Discontinuation of Vaccination for Individual Participants

No.	Item
1.	Grade 2 or greater hypersensitivity believed by the PI to be related to the vaccine, eg, anaphylaxis, allergic reaction
2.	Any Grade 3 or higher systemic reactogenicity symptom assessed by e-diary and confirmed by the PI
3.	Any AE that would pose a risk to the participant as determined by the PI if continued vaccinations were to occur
4.	Any violation of eligibility criteria discovered after randomization that would pose a risk to the participant, as determined by the PI and agreed by the MM
5.	Febrile illness (fever > 100.4 °F) within three days prior to any vaccination (Exception: The vaccination visit may be rescheduled to another day outside this three-day period providing it will not fall outside the required visit window for the visit [refer to Section 8.1].)
6.	Receipt of IP associated with loss of cold chain

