Study Day (Visit Window in Days)	-28 to -2						43 (±2), 120 (±14), 211 (±14), 302 (±14), 394 (±14)	-	On unscheduled visit days: X _{<D64} = assessment to be performed only if before Day 64.
Vaccination		X	X	X					IP will be prepared by an unblinded member of site staff on Day 1. Participants will be vaccinated (by an unblinded member of site staff) as assigned by randomization on Day 1, followed by 30-minute observation (by a blinded member of site staff) for adverse effects of vaccination especially anaphylaxis.
Provision and instructions on use of the following: hand-held device, oral thermometer and injection site reaction measurement tool		X							A hand-held device will be provided only to those participants who do not have or do not wish to use their own personal device. Instructions on use of hand-held device, oral thermometer and injection site reaction measurement tool will be provided on Day 1 post-vaccination.
Participant e-diary entry		X→	→X→	X→					E-diary completion instructions and training will be provided on Day 1. Subjects will be instructed to complete the e-diary starting on the evening of Day 1 (with Day 1 being the day of first vaccination) and on every subsequent evening (for at least seven days). Participants are to complete the e-diary daily for at least seven days following each vaccination. If a reaction is not resolved at seven days postvaccination, the participant is to continue completing the e-diary daily until they are symptom free for two consecutive days.

Study Periods	Screening	In-clinic Visits					Safety Follow-up Phone Calls	Unscheduled Visit	Comments
		1	15 (±1)	29 (±2)	64 (±3)	EWV			
Study Day (Visit Window in Days)	-28 to -2						43 (±2), 120 (±14), 211 (±14), 302 (±14), 394 (±14)	-	On unscheduled visit days: X _{<D64} = assessment to be performed only if before Day 64.
E-diary review by PI/site staff			→X	→X→		X	X (Day 43 only)	X _{<D64}	Site staff will assess e-diary data daily and review it with participants at the Day 15 and 29 visits, as well as at unscheduled visits occurring before Day 64 and EWV if applicable. On Day 43 (±2 days), site staff will follow-up with a telephone call to review e-diary data entered by the participant after Day 29.
Collect hand-held device					X	X			The hand-held device will be collected from any applicable participants who did not already return it using the provided return packaging.

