If the original (retested sample) or repeat laboratory value is Grade 3 or higher, this will be considered an AE and will be recorded by the PI on the AE eCRF. Any other clinical laboratory abnormalities must also be reported as AEs if considered by the PI or designee to be a clinically significant change from baseline. As toxicity grading is being used in this study to evaluate and record AE severity (refer to [Section 9.2.1](#)), the lab toxicity grade is to be assigned as the AE toxicity grade when reporting on the AE eCRF. If the lab analyte does not have toxicity grading criteria specified in [Table 9](#), then the PI or designee will use the grading criteria for “illness or clinical AE” in [Table 8](#) to assign the AE toxicity grading. If an abnormal laboratory test result is a sign of a disease or syndrome, the disease or syndrome will be recorded as the AE/SAE and not the abnormal laboratory result. Clinical laboratory abnormalities may trigger study halting rules (see [Section 7.1](#)) and will require discontinuation of vaccinations in an individual participant if considered associated with vaccination (see [Section 7.3](#)).

Table 7: Screening/Safety Clinical Laboratory Tests

Hematology -Basophils -Eosinophils -Hematocrit -Hemoglobin -Lymphocytes -Monocytes -Neutrophils -Platelets -RBC count -WBC count Serum Chemistry -ALP -ALT -AST -Bilirubin, Total -BUN -Creatinine -Glucose, nonfasting	Urinalysis -Appearance -Bilirubin -Color -Glucose -Ketones -Leukocyte esterase -Nitrite -Occult blood -pH -Protein -Specific gravity -Urobilinogen -Microscopic examination (only if protein, nitrite, leukocyte esterase, or occult blood results are positive) Additional Tests -FSH (only in women having > 12 consecutive months without menses to confirm postmenopausal status) -Serum/urine pregnancy test (WOCBP only; also suspected postmenopausal women at Screening only) -TSH	Viral Serology: -anti-HCV antibody -anti-HIV antibody -HBsAg Urine Drug Screen: -Amphetamines -Barbiturates -Benzodiazepines -Cannabinoids -Cocaine -Opioids Autoantibodies -RF -ANA -anti-dsDNA antibodies
---	---	--

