If injection site or systemic reactions continue beyond seven days, participants will be prompted to continue e-diary entries until they are symptom-free for two consecutive days. For any type of reactogenicity persisting two weeks or more, the PI or designee will evaluate the reaction at the next scheduled visit and/or determine based on the nature and severity if a more immediate unscheduled follow-up visit is required to fully assess the reaction. Investigational sites will be alerted of any Grade 3 or higher (eg, ER visit or hospitalization) solicited systemic reactions, which will require discontinuation of vaccinations upon verification by the PI or designee of the Grade 3 or higher status. The PI or designee may require participants reporting Grade 3 or higher reactions to return to the clinic for an unscheduled visit to aid in this evaluation.

In addition to any reaction considered an AE by the PI, solicited reactions reported in the e-diary will be recorded by the PI or designee on the AE eCRF if they are serious [ie, a solicited reaction will be considered ‘serious’ if confirmed by the investigator to be a Grade 4, or a Grade 3 that upon the investigator’s assessment meets any of the SAE criteria outlined in [Section 9.1.2](#)]; result in discontinuation of study product or withdrawal from the study; or remain unresolved for 14 days or more. Solicited systemic reactions may require discontinuation of vaccinations based on individual participant halting rules (see [Section 7.3](#)).

The rating scale to be used for reactogenicity events is the same toxicity grading scale provided in [Appendix A](#), the FDA Guidance for Industry: *Toxicity Grading Scale for Healthy Adult and Adolescent Volunteers Enrolled in Preventive Vaccine Clinical Trials* {[CBER, 2007](#)}, where symptoms are assessed as Grade 1=mild through Grade 4=potentially life-threatening. Additionally, a Grade of 0 will be available in the e-diary in order to allow the participant to record “symptom not present.” For most of the reactogenicity events, there is a direct

corresponding symptom entry in the toxicity grading scale (eg, for systemic reactions: fever, headache, fatigue, myalgia; for local reactions: pain, tenderness, erythema/redness, induration/swelling) – refer to [Table 8](#).

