9.2. Eliciting and Reporting Adverse Events

AEs (including SAEs and potential AESIs) reported spontaneously by the participant and/or in response to an open question from the PI or designee or revealed by observation (eg, during PE or from a clinical test result) will be recorded by the PI or designee on the AE eCRF if they

occurred from the time of the first vaccination on Day 1 up to Month 13, regardless of causal association with the IP. AE reporting is required for any new observation presenting after the first vaccination or for a deterioration of baseline condition (eg, increased severity/frequency). From the signing of the ICF until immediately before the first vaccination on Day 1, only AEs resulting from a study-related procedure will be recorded on the AE eCRF; all other events reported in this time period will be recorded as signs and symptoms on the Medical History eCRF. If there is any doubt as to whether a clinical or laboratory observation is an AE, the event will be considered an AE and recorded on the AE eCRF.

Refer to the specific sections on clinical laboratory tests ([Section 8.3.2](#)), PEs ([Section 8.3.3](#)), vital signs ([Section 8.3.4](#)), and e-diary reactogenicity ([Section 8.3.5.1](#)) for details on AE reporting based on participant observation and clinical test results.

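### After injection 3 (saline for AV7909, active for BioThrax) a non-serious Grade 3 solicited systemic reaction under 14 days is no longer a mandatory AE entry, so mandatory capture covers 2 of 2 active AV7909 doses but 2 of 3 active BioThrax doses (low priority)

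*Protocol*

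**What the plan says.** Two protocol rules interact.

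- **Halting rule.** Table 5 item 2 (Protocol 7.3.1) lists, as a reason to stop vaccination permanently, "Any Grade 3 or higher systemic reactogenicity symptom assessed by e-diary and confirmed by the PI". Section 8.3.5.1 says the same of Grade 3 or higher solicited systemic reactions, "which will require discontinuation of vaccinations upon verification by the PI or designee of the Grade 3 or higher status".
- **AE entry rule.** Under 8.3.5.1 a solicited reaction goes on the AE eCRF if it is serious, or if it should "result in discontinuation of study product or withdrawal from the study; or remain unresolved for 14 days or more". Grade 4 always counts as serious. Grade 3 does so only if it meets an SAE criterion. These triggers apply "In addition to any reaction considered an AE by the PI", so the PI may enter any other reaction. SAP 2.2.3.5 repeats the triggers and adds nothing for the third injection.

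On dosing, the synopsis states: "Saline for injection will be administered SC on Day 29 in Groups 1 to 3 to mask the vaccine schedule". Group 4 receives active BioThrax on Days 1, 15 and 29.

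Three provisions encourage entry after injection 3. Sites are alerted to Grade 3 or higher systemic reactions (8.3.5.1). On Day 43, "site staff will follow-up with a telephone call to review e-diary data entered by the participant after Day 29" (Table 6). When it is doubtful whether an observation is an AE, "the event will be considered an AE and recorded on the AE eCRF" (9.2).

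On reporting, SAP 7.2.1 has rows for Grade 3 or 4 TEAEs and for vaccine-related Grade 3 or higher TEAEs, shown for pooled AV7909 beside BioThrax. SAP 7.7.1 tabulates e-diary reactions by grade after each vaccination.

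**The concern.** For a non-serious Grade 3 systemic reaction of under 14 days, the only compulsory routes to the AE eCRF are discontinuation and study withdrawal. The first exists only while another injection is scheduled. The rule is worded identically for every arm, but the injection at which it lapses is inert in one arm and active in the other.

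Elsewhere the protocol uses grade itself as the trigger, for example for laboratory results: "If the original (retested sample) or repeat laboratory value is Grade 3 or higher, this will be considered an AE". Grade 3 or higher vital signs are treated in the same way (8.3.4). For solicited systemic reactions the grade trigger works only through the halting rule, and neither document gives a reason for letting it end with dosing.

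At stake is the comparability of the two Grade 3 rows and, to a lesser degree, of the all-TEAE row. AEs from Day 1 to Day 64 are a secondary safety endpoint (Protocol 3.2.2). AE eCRF entry also decides whether a severe event reaches the DSMB Chair as a matter of course (8.4.1).

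**Working it through.** The plan states no figure on this point, so there is none to reproduce.

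**Step 1: count of active doses.** The discontinuation trigger can act only if a later injection is scheduled.

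| Injection | AV7909 | BioThrax | Later injection scheduled? | Entry compulsory for a PI-confirmed, non-serious Grade 3 systemic reaction under 14 days? |
|---|---|---|---|---|
| 1 (Day 1) | active | active | yes | yes |
| 2 (Day 15) | active | active | yes | yes |
| 3 (Day 29) | saline | active | no | only if the participant withdraws |

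Active doses covered: AV7909 2 of 2, BioThrax 2 of 3. SAP 5.1 supports this reading, since it counts a participant who has received all vaccinations as having completed treatment.

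**Step 2: possible size.** The documents give no Grade 3 systemic rate per dose, so every input here is an assumption:

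- g: rate of such reactions per active BioThrax dose, the same at each dose and independent between doses
- b: share of participants already in the row for another AE, independent of g
- q: share of injection-3 events that the PI enters by judgement
- saline inert, and everyone without an earlier Grade 3 systemic reaction receives injection 3

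BioThrax row with complete capture: 1 − (1−b)(1−g)³.

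BioThrax row as recorded: 1 − (1−b)[(1−g)² − q·g·(1−g)²].

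Shortfall = (1−q)(1−b)·g·(1−g)². It does not involve the AV7909 rate.

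With q = 0 and b = 10%:

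| g | Shortfall | Points | Of 550 |
|---|---|---|---|
| 1% | 0.9 × 0.01 × 0.9801 | 0.88 | 4.9 |
| 2% | 0.9 × 0.02 × 0.9604 | 1.73 | 9.5 |
| 5% | 0.9 × 0.05 × 0.9025 | 4.06 | 22.3 |

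At b = 0 the points are 0.98, 1.92 and 4.51; at b = 20% they are 0.78, 1.54 and 3.61.

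**Step 3: effect on the row ratio.** Suppose per-dose rates are equal and b = 10%. The AV7909/BioThrax ratio as recorded at q = 0 is then 1.00. Complete capture would give 11.79/12.67 = 0.93, 13.56/15.29 = 0.89 and 18.77/22.84 = 0.82.

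**Step 4: what shrinks it.**

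- PI-judged entry: multiply by (1−q). At q = 0.9 and b = 10%, about 0.5, 1 and 2 of 550 remain.
- Drop-out before injection 3: multiply by the share who reach it.
- Reactions to saline at half the active rate, with equal active rates: the net shortfall halves to 0.44, 0.86 and 2.03 points.
- Combined example at g = 1%, b = 10%, q = 0.5 and 10% not reaching injection 3: 0.88 × 0.5 × 0.9 ≈ 0.4 points, about 2 participants.

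**The case against.** The strongest reply is that 8.3.5.1 sorts solicited reactions by consequence, not by grade. A reaction with no consequence stays in the e-diary, where it is already a secondary endpoint tabulated by grade and vaccination. Comparing two-dose and three-dose regimens will always give some imbalance, and this one runs against the investigational product. All of that is fair. It is why the point is minor, but it does not make the two columns of the Grade 3 rows comparable.

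A second reply is that 9.2 calls for AE reporting of any new observation after the first vaccination, and that the alert, the Day 43 call and the Day 64 AE assessment give ample occasion to record. This stands in part. A reader might infer that Grade 3 reactions after the third BioThrax dose go unrecorded as AEs; the documents do not support that. Capture there is discretionary, not zero. But 9.2 refers back to 8.3.5.1 for e-diary reactions, and PI discretion across about 40 sites is not the same as automatic entry.

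A third reply is that the rates tried are too high. Protocol 2.2.3 describes systemic reactions to AVA plus CPG 7909 as mainly mild to moderate. None of the nine AEs that stopped dosing in EBS.AVA.208 was fever, headache, fatigue or muscle ache, and none arose in the AVA arm. That arm was small and dosed IM, so it does not settle the BioThrax SC rate, but nothing in the documents supports 5% per dose. In addition, within-person correlation would lower the third-dose rate, because earlier Grade 3 reactors have already stopped.

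**Conclusion.** The gap in mandatory capture is real and follows directly from the text: 2 of 2 active AV7909 doses against 2 of 3 active BioThrax doses. It can tilt the two descriptive Grade 3 rows modestly against AV7909, as long as an active third dose causes more such reactions than saline. The size is unknown. The figures of about 0.9, 1.7 and 4.1 points are an upper bound for their assumed g and for b = 10%, and rest on the conditions listed in Step 2 with q = 0.

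Three stronger readings should be avoided.

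- **That the safety comparison as a whole is compromised.** Serious reactions are entered after every injection, so the SAE endpoint is intact. No formal test uses these rows. The e-diary tables and the table of TEAEs leading to discontinuation (SAP 7.2.5) are unaffected.
- **That the ratio moves from about 0.67 to 1.00.** That holds only for the solicited component alone (b = 0, q = 0, equal rates). The actual rows also contain unsolicited, laboratory and vital-sign AEs.
- **That the study halting count is blind to these events.** Section 8.3.5.1 has sites check e-diary entries against the study halting rules.

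This is a low-priority improvement.

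**What to change.** **While dosing continues.** In Protocol 8.3.5.1, and where SAP 2.2.3.5 repeats it, require AE eCRF entry of every PI-confirmed Grade 3 or higher solicited systemic reaction after any of the three injections. Mandatory capture becomes 2 of 2 and 3 of 3 active doses. The text is one sentence, but it is a protocol amendment needing IRB/IEC approval, and a change mid-trial would mix two capture rules in one row. It adds at most about 5, 11 or 25 entries among 550 BioThrax participants at g = 1%, 2% or 5% (550 × g × (1−g)²). If saline reacts at half the active rate, it also adds up to about 16, 32 or 75 among 3300 AV7909 participants. These events would appear in both the TEAE and e-diary tables.

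**If dosing is complete.** The duplicate-enrolment text in SAP 4.9.2 and Appendix IV suggests it may be. In that case show the Grade 3 or 4 and vaccine-related Grade 3+ rows of SAP 7.2.1 with and without AEs of solicited origin, with a footnote to the e-diary table. Take out such AEs from all three injections. Removing only those that led to discontinuation would leave PI-judged entries from injection 3 in the row. The cost is matching AE records to e-diary records by participant, symptom and date, since the documents describe no eCRF flag for solicited origin. No new participant assessments are needed.

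Neither route changes Grade 3 injection-site reactions. The halting rule does not cover them, so no such break occurs at injection 3 and their entry can stay as it is.

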8.4. Data Monitoring Committee(s)

8.4.1. Data Safety Monitoring Board

Independent safety oversight will be provided by a DSMB, which will be notified of significant AEs (eg, SAEs, severe AEs recorded on eCRF, potential AESIs of autoimmune etiology, or any other events the MM deems medically relevant) as determined by the MM on an ongoing basis, including any that result in study halt based on prespecified stopping rules (refer to [Section 7.1](#)). The DSMB will comprise at least three voting members, to include one expert in immunology to specifically support the evaluation of potential AESIs for autoimmune etiology.

All DSMB reviews will be performed with blinded data, unless otherwise requested by the DSMB Chair. The DSMB will make recommendations regarding the safety of continuing enrollment and dosing. Study enrollment and dosing may be interrupted at the request of the DSMB Chair if it is believed that an AE represents a significant safety concern requiring interruption of dosing pending full DSMB evaluation.

A planned interim DSMB safety data review will be conducted after the first 500 participants have completed the Day 29 visit, comprising all safety evaluations through two weeks after the second vaccination. The DSMB will be supported by a (non-voting) unblinded statistician who will provide safety data (also demographics/baseline characteristics and protocol deviations) and otherwise assist in review activities as required.

The DSMB Chair will receive and evaluate each SAE, each severe AE (reported on the AE eCRF), and potential AESIs of autoimmune etiology. In addition, the MM may notify the DSMB Chair of any other medically relevant events (based on regular medical monitoring activities) for their review. The DSMB Chair will determine if an *ad hoc* review, in addition to the planned interim review, by the entire DSMB is necessary. An *ad hoc* review by the entire DSMB, when it occurs, may be focused on a single participant or on data for all participants. The operations of

the DSMB will be detailed in a DSMB Charter, to be finalized prior to screening of the first participant.

At least one DSMB member will be an expert in autoimmune disorders (eg, rheumatologist, immunologist). This member will review, on a blinded basis, all potential AESIs to assess cases for autoimmune etiology, if pre-existing or new onset, and relationship to the IP. Details on the recording of the AESI assessment outcomes will be detailed in the DSMB Charter.

